9. ANALYSES

9.1. The non-inferiority margin

The time to relapse hazard ratio and 95% confidence interval for CQ only versus PQ+CQ in DETECTIVE Part 1 is 3.68 (1.84 to 7.35). This can be considered a comparison of PQ versus placebo given CQ only treats the acute parasitemia, so does not prevent relapse. [Table 1](#) presents a range of preserved effects (preserving the difference versus placebo) based on the lower bound of the 95% confidence interval of 1.84. For example, a preserved effect of 50% would result in a non-inferiority margin of 1.42.

Table 1 Non-inferiority margins for a range of preserved effects.

No preserved effect	50%	66%	75%	80%	100%
1.84	1.42	1.29	1.21	1.17	1.00

The binary relapse/relapse-free data at six months, which contributes to the overall hazard ratio of 1.21, translates to an odds ratio of 1.45 (see Section 9.5).

The combined DETECTIVE Part 2 and GATHER sample size is expected to be 642, with 428 on TQ+CQ and 214 on PQ+CQ. Based on these figures, if the PQ+CQ efficacy is 60.3% then an odds ratio of 1.45 equates to a PQ+CQ minus TQ+CQ efficacy difference of 9.1%. Table 2 shows the PQ+CQ minus TQ+CQ percentage differences for a range of efficacies.

Table 2 PQ+CQ minus TQ+CQ percentage differences for a range of efficacies (based on an odds ratio of 1.45).

PQ efficacy (%)	TQ efficacy (%)	Difference (%)
40.2	31.8	8.4
50.0	40.9	9.1
60.3	51.2	9.1
70.1	61.9	8.2
80.4	73.8	6.5

During discussions with the clinical team on 7th September 2016 a preserved effect of 75% was chosen, resulting in a non-inferiority margin of 1.21. This value is considered not to represent a clinically meaningful difference. Section 9.2 contains details about the statistical reasoning underpinning the selection of the non-inferiority margin.

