9.3. Is the non-inferiority margin reasonable?

To ensure the non-inferiority margin selected from DETECTIVE Part 1 is consistent with published literature on PQ+CQ the odds and risk ratios, adjusted for region, for PQ+CQ versus CQ only relapse in DETECTIVE Part 1 were also calculated.

Based on all subjects who completed six months of follow-up in DETECTIVE Part 1 there were 12/40 relapses in the PQ+CQ arm and 30/42 relapses in the CQ only arm. This translates to an adjusted odds ratio (95% confidence interval) of 0.12 (0.04 to 0.36) and an adjusted risk ratio (95% confidence interval) of 0.42 (0.21 to 0.82).

- In the Worldwide Antimalarial Resistance Network's (WWARN) Primaquine Review³ the odds ratio (95% confidence interval) for low dose PQ was 0.14 (0.06 to 0.35).

- In the Cochrane systematic review⁴ of ‘Primaquine for preventing relapse in people with *Plasmodium vivax* malaria treated with chloroquine’ the risk ratio (95% confidence interval) for supervised 14-day PQ treatment with follow-up for less than or equal to 6-months was 0.40 (0.23 to 0.68).

The DETECTIVE Part 1 results are consistent with the published literature, and support the use of the study to determine the non-inferiority margin as a hazard ratio for use in the planned meta-analysis.

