9.4. Meta-analysis

Using the individual subject level data from the TQ+CQ and PQ+CQ arms of DETECTIVE Part 2 and GATHER, a Cox proportional hazards model will be fitted with region, study and treatment as covariates. The hazard ratio of TQ+CQ versus PQ+CQ, plus the associated 95% confidence interval and p-value, will be presented. The upper bound of the 95% confidence interval will be compared to the non-inferiority limit of 1.21 and interpreted as outlined in Section 6.

Interactions between study and treatment, and region and treatment will be assessed at the 10% (2-sided) level of significance. If any significant interactions are identified from the Cox proportional hazards model, they may be further investigated by presentation of the time-to-relapse hazard ratios and 95% confidence intervals for each study and/or region separately.

A Kaplan-Meier survival curve with 95% confidence bands and a log-log plot will be produced.

An important assumption underpinning the Cox proportional hazards model is that of proportional hazards. The proportional hazards assumption will therefore be assessed and will include a visual check of the Kaplan-Meier curves. The shape of the curves should be similar for the TQ+CQ and PQ+CQ treatment groups with the separation between the curves remaining proportional across time. A complementary log-log plot will also be used to check the proportional hazards assumption. In this plot both treatment group lines should appear approximately linear.

In the event that the proportional hazards assumption is considered violated the primary comparison will be based on a logistic regression model. The treatment difference will then be assessed for non-inferiority based on the upper bound of the 95% confidence interval surrounding the odds ratio. Further details in Section 9.5.

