9.5. Odds ratio

The odds ratio, adjusted for study and region, will be presented along with the 95% confidence interval. However it will **only** be formally assessed for non-inferiority **if** the proportional hazards assumption (described in Section 9.4) is violated.

The non-inferiority margin for the odds ratio has been calculated using the same methodology described for the hazard ratio in Section 9.2. In brief, the lower bound of the DETECTIVE Part 1 CQ only versus PQ+CQ odds ratio is used to identify M1, the

starting point for identifying the non-inferiority margin. The non-inferiority limit, M2, has then been selected to maintain a specified preserved amount that translates to a value considered not to represent a clinically meaningful difference.

Table 3 shows the odds ratio non-inferiority margin for a range of preserved effects. The non-inferiority margin for the odds ratio is 1.45 (for the 75% preserved effect, consistent with that used for defining NI margin for the survival analysis). These values were agreed by the clinical team at a meeting on 7th September 2016.

Table 3 Odds ratio non-inferiority margin for a range of preserved effects

Actual (PQ+CQ vs CQ only)			Reciprocal (CQ only vs PQ+CQ)			Preserved Effects					
Ratio	LB	UB	Ratio	LB	UB	No	50%	66%	75%	80%	100%
0.12	0.04	0.36	8.66	2.80	26.85	2.80	1.90	1.61	1.45	1.36	1.00

The odds ratio will be adjusted for both study and region using a logistic regression model. Interactions between study and treatment, and region and treatment will be assessed at the 10% (2-sided) level of significance. If any significant interactions are identified they may be further investigated by presentation of the odds ratio and 95% confidence intervals for each study and/or region separately.

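### The meta-analysis plan treats a hazard-ratio margin of 1.21 and an odds-ratio margin of 1.45 as equivalent; they are not, and a visual check can move the decision to the looser one

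*Supplement*

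**What the plan says.** The primary test compares tafenoquine (TQ+CQ) with primaquine (PQ+CQ) on time to relapse over six months. The upper 95% confidence bound of the Cox hazard ratio is set against a fixed margin (Meta-Analysis Plan, Sections 6 and 9.4). For that margin, Section 9.1 reports that "a preserved effect of 75% was chosen, resulting in a non-inferiority margin of 1.21". Just before this it states: "The binary relapse/relapse-free data at six months, which contributes to the overall hazard ratio of 1.21, translates to an odds ratio of 1.45". That sentence ends with a cross-reference to Section 9.5. Table 2 then shows what an odds ratio of 1.45 means as a loss of six-month efficacy. It is the only table in the plan that puts a margin in absolute terms, and the text after it judges 1.21 not to be a clinically meaningful difference.

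Section 9.5 derives 1.45 from the Part 1 odds ratio and calls the 75% preserved effect "consistent with that used for defining NI margin for the survival analysis".

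On the choice between the two, Section 9.4 says: "In the event that the proportional hazards assumption is considered violated the primary comparison will be based on a logistic regression model". The assessment of proportional hazards "will include a visual check of the Kaplan-Meier curves" by treatment group and a complementary log-log plot. The plan gives no test, level or threshold and names no independent assessor. Section 9.5 adds that the odds ratio is always presented but is formally assessed for non-inferiority only if the assumption fails.

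**The concern.** If 1.21 really translated to 1.45, two things would follow. Table 2 would be a fair clinical justification of the primary margin, and a switch from one scale to the other would leave the standard of proof unchanged. If the two margins differ, neither holds. Readers who judge 1.21 from Table 2 are shown the losses allowed by another margin. The check of proportional hazards also becomes a choice between a stricter and a looser non-inferiority test, made from plots that display the very comparison being tested. Non-inferiority is the plan's primary objective, so the decision rule has to be unambiguous.

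**Working it through.** **Inputs (Meta-Analysis Plan).** Part 1 lower bounds for CQ only versus PQ+CQ: hazard ratio 1.84 (Section 9.1) and odds ratio 2.80 (Section 9.5, Table 3). Preserved effect 75%. PQ efficacies from Table 2. Expected sample 428 TQ+CQ and 214 PQ+CQ (Section 9.1). Two-sided 95% interval, that is 2.5% one-sided.

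**1. Reproduce the plan's margins.** Margin = 1 + (1 − 0.75) × (M1 − 1).
- Hazard ratio: 1 + 0.25 × 0.84 = 1.21.
- Odds ratio: 1 + 0.25 × 1.80 = 1.45.

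Both agree with the plan, as do the other columns of Tables 1 and 3. Table 2 also reproduces, within 0.1 point in every row, from TQ odds = PQ odds / 1.45. So 1.45 is a second margin with its own starting bound and is not a conversion of 1.21.

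**2. Convert one margin to the other.** Under proportional hazards with complete follow-up to six months, TQ efficacy = (PQ efficacy)^1.21. The equivalent odds ratio is [PQ/(1 − PQ)] / [TQ/(1 − TQ)]. In reverse, the hazard ratio implied by 1.45 is ln(TQ)/ln(PQ), with TQ taken at odds ratio 1.45. At PQ 60.3%: 0.603^1.21 = 0.542, a loss of 6.1 points, and (0.603/0.397)/(0.542/0.458) = 1.28.

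| PQ efficacy (%) | TQ at HR 1.21 (%) | Loss at HR 1.21 (points) | Loss in Table 2, OR 1.45 (points) | OR equal to HR 1.21 | HR equal to OR 1.45 |
|---|---|---|---|---|---|
| 40.2 | 33.2 | 7.0 | 8.4 | 1.35 | 1.26 |
| 50.0 | 43.2 | 6.8 | 9.1 | 1.31 | 1.29 |
| 60.3 | 54.2 | 6.1 | 9.1 | 1.28 | 1.32 |
| 70.1 | 65.1 | 5.0 | 8.2 | 1.26 | 1.36 |
| 80.4 | 76.8 | 3.6 | 6.5 | 1.24 | 1.39 |

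No row gives 1.45. The loss in Table 2 is 1.2 times (8.4/7.0) to 1.8 times (6.5/3.6) the loss that 1.21 allows. In Part 1, 12 of 40 PQ subjects who completed six months relapsed (Section 9.3), so 70% were relapse-free; at the neighbouring 70.1% row the figures are 8.2 and 5.0 points.

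**3. Consequence if the switch is made.** Take a true hazard ratio of exactly 1.21 with hazards proportional. The chance that the odds-ratio test succeeds is Φ{[ln 1.45 − ln(equivalent OR)]/SE − 1.96}, with SE² = 1/[428·TQ(1 − TQ)] + 1/[214·PQ(1 − PQ)]. At 60.3%, SE = 0.170, and Φ{(0.372 − 0.248)/0.170 − 1.96} is about 11%. Over the five rows the results are about 6, 9, 11, 12 and 12%, against 2.5% for the hazard-ratio test. A binomial simulation of 200,000 runs gave 8.5, 11.0, 12.2 and 11.8% for the last four rows.

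**4. Chance of success if the drugs are equal, PQ 60.3%.**
- Cox, margin 1.21: events = 0.397 × 642 = 255 and SE = 1/√(255 × 2/9) = 0.133, giving about 30%.
- Odds ratio, margin 1.45: SE = 0.171, giving about 58%.
- Odds ratio, margin 1.28 (matched to 1.21): about 31%.

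Nearly all of the gap between 30% and 58% therefore comes from the looser margin and not from the change of model.

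**The case against.** Each margin is correctly computed by a disclosed rule. Table 3 prints the 2.80, the sentence in Section 9.1 points to Section 9.5, and Table 2 is labelled as based on 1.45. A reader might infer an arithmetic error, but the documents do not support that. The fault is the claimed equivalence and the use of Table 2 beside 1.21.

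A reader might also infer that the trial's error rate is 11%. It is not. The odds ratio decides only if proportional hazards is judged violated. If that happened wrongly in 10 to 20% of trials, independently of the result (an assumption; the plan gives no figure), the overall error at 60.3% would be 0.9 × 2.5 + 0.1 × 10.8 = 3.3% up to 0.8 × 2.5 + 0.2 × 10.8 = 4.2%. Where hazards are truly non-proportional, no single true hazard ratio exists to serve as the null.

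The gap is also smaller at low PQ efficacy (8.4 against 7.0 points at 40.2%). On the log scale the two margins preserve 69% and 64% of their bounds. The fallback was specified in advance, and the plan places its decisions before database lock. The check uses a log-log plot as well as Kaplan-Meier curves. Both ratios are presented whichever one governs, so a switch would be visible.

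All of this stands, and it limits the size of the point. It does not make the margins equivalent, and it does not supply a criterion for the switch: the log-log plot is visual too. The plan does not call the check unblinded, but plots split by TQ+CQ and PQ+CQ show the treatment comparison to whoever judges them.

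**Conclusion.** The point holds in this form. The statement that 1.21 translates to 1.45 is wrong at every PQ efficacy in the plan's own table, and Table 2 overstates the loss allowed by the primary margin by 1.4 to 3.2 points. The plan also lets an uncriterioned visual judgement replace the primary margin with a looser one. The 6 to 12% figure applies only when the switch is made although hazards are proportional. The primary Cox rule is unaffected if no switch occurs.

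The conversions assume proportional hazards and complete six-month follow-up. The error and power figures use a normal approximation, crude odds ratios and all 642 subjects. The primary population is per protocol, and subjects censored early drop out of the logistic model, so the actual numbers will be smaller. With 20% fewer subjects the 11% becomes about 9%. Adjustment for study and region would shift the odds ratio somewhat.

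**What to change.** In Section 9.1, delete the claim of translation and state that 1.45 is a separate margin, derived from the Part 1 odds ratio and looser than 1.21. Add to Table 2 the losses for the hazard-ratio margin: 7.0, 6.8, 6.1, 5.0 and 3.6 points. In Sections 9.4 and 9.5, keep the Cox hazard ratio against 1.21 as the single non-inferiority rule and make the odds ratio supportive only.

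If a binary fallback is kept, base its margin on the same absolute six-month loss as 1.21 at a PQ efficacy fixed in advance, and set an objective trigger before unblinding. This is the weaker option. It obtains that loss through proportional hazards, the assumption that would just have been rejected, and it needs a planning PQ rate, which the plan does not name.

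The change costs only wording if made before database lock. The price is a fallback that is harder to pass: about 31% instead of 58% when the drugs are equal and PQ efficacy is about 60%. With a single Cox rule, a hazard ratio under non-proportional hazards is an average over follow-up and should be read beside the Kaplan-Meier curves and the odds ratio.

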9.2. How the non-inferiority margin was defined

The data from DETECTIVE Part 1 was used to select the non-inferiority margin as a hazard ratio using the following steps.

[figure not shown]
Step 1: The hazard ratio and 95% confidence interval for CQ only versus PQ+CQ was determined from a Cox proportional hazards model using region as a covariate. India was excluded from the primary efficacy analyses in the study due to very low relapse rates across all study treatment groups.

Step 2: The lower bound of the confidence interval identified an amount, M1, which acted as the starting point for determining the non-inferiority margin.

Step 3: The non-inferiority margin, M2, was then chosen to ensure a specified preserved effect of PQ+CQ over CQ only that translates to a value considered not to represent a clinically meaningful difference.

The approach taken to define the non-inferiority limit is shown graphically in Figure 3 and is based on the methods described in Schumi (2011).

Figure 3 Determining the non-inferiority margin (M2 represents the non-inferiority margin and M1 represents the lower bound of the 95% confidence interval of the hazard ratio comparing CQ only versus PQ+CQ in DETECTIVE Part 1).

The results from DETECTIVE Part 1 have been used to determine the non-inferiority margin as a hazard ratio because similar comparisons of PQ+CQ in the published literature are limited.

An alternative approach would have been to perform the primary comparison as a binary (relapse/no relapse) endpoint. The decision was taken to base the primary approach using survival analysis as this makes the most use of the individual patient level data available.

9.3. Is the non-inferiority margin reasonable?

To ensure the non-inferiority margin selected from DETECTIVE Part 1 is consistent with published literature on PQ+CQ the odds and risk ratios, adjusted for region, for PQ+CQ versus CQ only relapse in DETECTIVE Part 1 were also calculated.

Based on all subjects who completed six months of follow-up in DETECTIVE Part 1 there were 12/40 relapses in the PQ+CQ arm and 30/42 relapses in the CQ only arm. This translates to an adjusted odds ratio (95% confidence interval) of 0.12 (0.04 to 0.36) and an adjusted risk ratio (95% confidence interval) of 0.42 (0.21 to 0.82).

- In the Worldwide Antimalarial Resistance Network's (WWARN) Primaquine Review³ the odds ratio (95% confidence interval) for low dose PQ was 0.14 (0.06 to 0.35).

- In the Cochrane systematic review⁴ of ‘Primaquine for preventing relapse in people with *Plasmodium vivax* malaria treated with chloroquine’ the risk ratio (95% confidence interval) for supervised 14-day PQ treatment with follow-up for less than or equal to 6-months was 0.40 (0.23 to 0.68).

The DETECTIVE Part 1 results are consistent with the published literature, and support the use of the study to determine the non-inferiority margin as a hazard ratio for use in the planned meta-analysis.

9.4. Meta-analysis

Using the individual subject level data from the TQ+CQ and PQ+CQ arms of DETECTIVE Part 2 and GATHER, a Cox proportional hazards model will be fitted with region, study and treatment as covariates. The hazard ratio of TQ+CQ versus PQ+CQ, plus the associated 95% confidence interval and p-value, will be presented. The upper bound of the 95% confidence interval will be compared to the non-inferiority limit of 1.21 and interpreted as outlined in Section 6.

Interactions between study and treatment, and region and treatment will be assessed at the 10% (2-sided) level of significance. If any significant interactions are identified from the Cox proportional hazards model, they may be further investigated by presentation of the time-to-relapse hazard ratios and 95% confidence intervals for each study and/or region separately.

A Kaplan-Meier survival curve with 95% confidence bands and a log-log plot will be produced.

An important assumption underpinning the Cox proportional hazards model is that of proportional hazards. The proportional hazards assumption will therefore be assessed and will include a visual check of the Kaplan-Meier curves. The shape of the curves should be similar for the TQ+CQ and PQ+CQ treatment groups with the separation between the curves remaining proportional across time. A complementary log-log plot will also be used to check the proportional hazards assumption. In this plot both treatment group lines should appear approximately linear.

In the event that the proportional hazards assumption is considered violated the primary comparison will be based on a logistic regression model. The treatment difference will then be assessed for non-inferiority based on the upper bound of the 95% confidence interval surrounding the odds ratio. Further details in Section 9.5.

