6. TREATMENT COMPARISONS

[figure not shown]
The primary comparison of interest is TQ+CQ versus PQ+CQ on the risk of relapse over the six month period post-dosing, with a primary objective of assessing non-inferiority. Superiority of TQ+CQ over PQ+CQ will be claimed if it exists.

The upper 95% confidence bound of the hazard ratio will be compared to a pre-specified non-inferiority margin (further details in Section 9). If the upper bound is:

- Less than one, then TQ+CQ will be declared both non-inferior and superior to PQ+CQ.
- Less than the non-inferiority limit and greater than one, then TQ+CQ will be declared non-inferior to PQ+CQ.
- Either equal to or greater than the non-inferiority limit, then non-inferiority between TQ+CQ and PQ+CQ has not been demonstrated.

Figure 1 shows the graphical interpretations of the possible TQ+CQ versus PQ+CQ hazard ratios and 95% confidence intervals.

Figure 1 Interpretation of the TQ+CQ versus PQ+CQ hazard ratio and 95% confidence interval (M2 represents the pre-determined non-inferiority margin).

For data displays, and throughout this document, treatment groups are defined using the following descriptors:

Treatment Group	Short Label Descriptor
Tafenoquine 300 mg + chloroquine	TQ+CQ
Primaquine + chloroquine	PQ+CQ
Chloroquine	CQ only

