11.2. Table of contents for Data Display Specifications

Population	Format	Example Shell	Title	Notes
All subjects randomised	Table	Table 1	Summary of Analysis Populations	
mITT and PP	Table	Table 2	Summary of Study Recruitment (by Study, Region and Country)	
mITT and PP	Table	Table 3	Summary of Demographic Characteristics	
mITT and PP	Table	Table 4	Analysis of time to relapse	
mITT and PP	Table	Table 5	Summary of Covariate and Interaction Significance from the Cox Proportional Hazards Model	
mITT and PP	Figure	Figure 1	Time-to-Relapse in the 6-month post-dosing period: Kaplan-Meier Survival Curves	
mITT and PP	Figure	Figure 2	Time-to-Relapse in the 6-month post-dosing period: log(-log(survival) versus log(time))	
mITT and PP	Table/Figure	Table 6	Adjusted Hazard Ratio and 95% Confidence Interval Forest Plot	

Population	Format	Example Shell	Title	Notes
mITT and PP	Table	Table 7	Analysis of Relapse during the 6-month post-dosing period (Missing on or after Day 29=Failure Sensitivity Analysis)	Only to be produced if proportional hazards assumption is violated for the time to relapse endpoint.
mITT and PP	Table	Table 8	Summary of Covariate and Interaction Significance from the Logistic Regression Model	
mITT and PP	Table	Table 8	Summary of Covariate and Interaction Significance from the Logistic Regression Model (Missing on or after Day 29=Failure Sensitivity Analysis)	Only to be produced if proportional hazards assumption is violated for the time to relapse endpoint.
mITT and PP	Table/Figure	Table 9	Adjusted Odds Ratio and 95% Confidence Interval Forest Plot	
mITT and PP	Table/Figure	Table 9	Adjusted Odds Ratio and 95% Confidence Interval Forest Plot (Missing on or after Day 29=Failure Sensitivity Analysis)	Only to be produced if proportional hazards assumption is violated for the time to relapse endpoint.
mITT and PP	Table	Table 10	Summary of Study Medication Compliance and Exposure	

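### The meta-analysis plan looks for straight lines on its log-log plot where proportional hazards calls for parallel ones, and this check helps decide which non-inferiority margin applies

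*Supplement*

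**What the plan says.** The primary analysis in the Meta-Analysis Plan (9.4) is a Cox model on the combined TQ+CQ and PQ+CQ data from DETECTIVE Part 2 and GATHER. Under section 6, "The upper 95% confidence bound of the hazard ratio will be compared to a pre-specified non-inferiority margin".

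Section 9.4 names two checks of proportional hazards:

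- The first is a look at the Kaplan-Meier curves, which should have similar shapes "with the separation between the curves remaining proportional across time".
- The second is the log-log plot: "A complementary log-log plot will also be used to check the proportional hazards assumption". Its reading rule follows at once: "In this plot both treatment group lines should appear approximately linear". Parallel lines are not mentioned.

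The axes are fixed by the display list in 11.2: "Time-to-Relapse in the 6-month post-dosing period: log(-log(survival) versus log(time)".

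The consequence is also in 9.4: "In the event that the proportional hazards assumption is considered violated the primary comparison will be based on a logistic regression model". Section 9.5 then judges the odds ratio against 1.45, and says that it is formally tested only in that event. No formal test of proportionality is given, and no rule for combining the two visual checks.

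The GATHER RAP (13.12.1.1) also mentions a complementary log-log plot but does not ask for straight lines. The sentence occurs only in the Meta-Analysis Plan.

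**The concern.** The plot is meant to test one assumption, but its reading rule describes another. Straightness on these axes belongs to the Weibull family. Proportionality is a relation between the two arms and says nothing about the shape of either. A reader who follows the sentence could cite bent lines as evidence against proportional hazards when the hazards are proportional, or straight lines as support when they are not.

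The stake is which test carries the non-inferiority claim. The check can move the claim from one effect measure and margin to another. The curves by arm can be drawn only after unblinding, so the criterion needs to be right in advance.

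**Working it through.** **1. The plan's margins.** Inputs are from 9.1 and 9.5: lower bounds M1 = 1.84 (hazard ratio) and 2.80 (odds ratio), with 75% of the effect preserved. The formula that reproduces Tables 1 and 3 is M2 = 1 + (M1 - 1) × (1 - 0.75).

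- Hazard ratio: 1 + 0.84 × 0.25 = 1.21, as stated ("resulting in a non-inferiority margin of 1.21").
- Odds ratio: 1 + 1.80 × 0.25 = 1.45, as stated.

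**2. What the plot shows under proportional hazards.** Write H(t) = -log S(t). If H1(t) = HR × H0(t) at every t, then log H1(t) - log H0(t) = log HR at every t. The curves are parallel for any H0. A single curve is straight against log(time) only if log H(t) = a + k log t, which is the Weibull form.

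**3. Proportional but not straight (illustration).** The documents give no hazard curve, so this baseline is an assumption: 0.0003 per day to day 30, 0.0045 to day 90, 0.0009 after.

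- H(180) = 0.009 + 0.270 + 0.081 = 0.360, so 69.8% are relapse-free.
- With HR = 1.21 the gap between curves is log 1.21 = 0.191 at every time.
- The local slope is log(0.0765/0.0087) / log(45/29) = 4.95 between days 29 and 45, and log(0.2925/0.279) / log(105/90) = 0.31 between days 90 and 105.

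The curves are clearly bent and exactly parallel. The bend depends on the assumption. A Weibull baseline gives none. A baseline with 2% relapse at day 0 and a constant hazard of 0.0019 per day gives only a mild one (slopes 0.51 to 0.94).

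**4. Straight but not proportional (illustration).** Take two Weibull arms with shapes 0.7 and 1.6 and the same H(180) = 0.357. Both lines are perfectly straight. The hazard ratio is (1.6/0.7) × (t/180)^0.9, which is 0.14 at day 8 and 2.29 at day 180.

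**5. How far apart the two margins are.** For PQ+CQ efficacy p (Table 2 values), TQ+CQ odds of staying relapse-free at the odds-ratio margin are [p/(1 - p)]/1.45. Convert these to efficacy q. The matching hazard ratio is log q / log p.

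| p | q at OR 1.45 | Matching HR |
|---|---|---|
| 60.3% | 51.2% | 1.325 |
| 70.1% | 61.8% | 1.355 |
| 80.4% | 73.9% | 1.387 |

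The q values agree with Table 2 to within 0.1 point. All three hazard ratios are above 1.21.

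**6. Effect on the chance of a positive claim.** This assumes no true difference, full follow-up, 428 and 214 subjects (9.1), and a normal approximation without covariates. The chance is Φ(log(margin)/SE - 1.96). For the hazard ratio SE² = 1/d1 + 1/d0, where d is relapses. For the odds ratio the reciprocals of the two relapse-free counts are added.

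| p | SE, HR | Chance on HR 1.21 | SE, OR | Chance on OR 1.45 |
|---|---|---|---|---|
| 60.3% | 0.133 | 30% | 0.171 | 58% |
| 70.1% | 0.153 | 24% | 0.183 | 53% |
| 80.4% | 0.189 | 17% | 0.211 | 42% |

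**The case against.** The strongest reply is that linearity does not decide the matter alone. The Kaplan-Meier check comes first in 9.4, the list of checks is not exhaustive, and the switch depends on an overall judgement that the assumption is violated. That stands. It also limits the second error: in the example with shapes 0.7 and 1.6, survival at day 60 is 84.8% against 94.0%, a gap of about 9 points that closes to zero by day 180. The Kaplan-Meier check should catch this.

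A reader might infer that the plan would reject proportional hazards in this trial because vivax relapse is not Weibull. The documents do not support that. They give no hazard curve for either arm, and the relapse intervals in protocol section 1.1 are for untreated infection. Nor would a formal goodness-of-fit test for straightness measure the plan's error rate, since the plan asks only for an approximate appearance, judged by eye.

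It is also fair that nothing is hidden. The hazard ratio and adjusted odds ratio are both presented in any case, and both margins were set before database lock. GATHER's own primary endpoint, haemolysis, is untouched.

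None of this makes the sentence correct. The Kaplan-Meier check is visual too, and with no rule for combining the checks, a wrong written criterion can be cited in support of either decision.

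**Conclusion.** The reading rule is wrong: on the stated axes proportional hazards means parallel curves, and straightness is neither necessary nor sufficient. This is algebra and needs no assumption about the data. The rule could count against valid proportional hazards or give false reassurance. How often either would happen cannot be settled from the documents, because it depends on the unknown baseline hazard and on a judgement by eye.

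The consequence can be sized. A switch moves the claim from a hazard-ratio margin of 1.21 to an odds-ratio margin equivalent to about 1.32 to 1.39 at PQ+CQ efficacies of 60.3% to 80.4%. Under the assumptions in step 6, the chance of showing non-inferiority with no true difference rises from 17% to 30% up to 42% to 58%. The hazard-ratio equivalents describe the size of the margins when hazards are proportional, which is the case in which a switch would be mistaken. Under 8.1 the logistic analysis also leaves out subjects censored before six months.

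This should be fixed. It is a fault in one sentence of the Meta-Analysis Plan, and it does not show that a wrong switch would follow.

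**What to change.** In Meta-Analysis Plan 9.4, replace the linearity sentence with: *In this plot the two treatment-group curves should be approximately parallel (constant vertical separation); they need not be linear.*

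Optionally, name a treatment-by-log(time) term or a scaled Schoenfeld residual test from the same Cox model as supporting evidence, and say how it and the two plots together lead to a finding of violation. This is a design choice beyond the correction itself.

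The correction costs one sentence. The optional test adds a line or so of code and a short decision rule. Neither needs new data or a change to the margins.
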